International and Ukrainian institutions have made significant commitments to increasing the quality of HIV/AIDS services, strengthening the capacity of Ukrainian institutions to improve the continuum of HIV services for key populations, and improving access to MAT. USAID and PEPFAR both currently support efforts to improve HIV case finding, primarily through increased HIV testing and initial linkage to care. Moreover, Ukraine has expanded availability of and access to MAT, a critical component of successful retention and care for PWID.^{20-23,44-48} Our proposed D2C strategy complements these efforts and leverages the expansion of MAT in Ukraine by identifying out-of-care HIV-positive PWID and linking them with HIV and other services, including MAT. The D2C intervention would be a valuable amendment that would increase the cost-benefit ratio of any case-management intervention by timely identifying patients who need it most.

A planning grant (R34) is the ideal mechanism for this developmental project. It will allow the research team to establish the feasibility of a D2C for PWID in Ukraine and develop the tools, protocols, and management structure for implementing a full-scale trial. It will also produce important planning information on the cost of implementing a D2C in Ukraine and allow us to determine under what conditions a D2C may be a reasonable investment in Ukraine. Finally, the proposed analytic strategy will inform sample size estimation for a larger trial and determine whether ordinal logistic regression, and more specifically mixed proportional odds models, may be suitable for modeling movement along the HIV care continuum among PWID.

The **scientific premise** of this project is strong. Only 29% of HIV-infected PWID in Ukraine are virally suppressed; of PWID who are on ART, only about 74% are undetectable.⁴⁹ Connecting PLWH who are diagnosed to comprehensive case management and ancillary services can improve outcomes along the HIV care continuum. Clinical and service provision data, including viral suppression, ART prescription, medical visits, and engagement in other services, can be used to improve health outcomes for HIV-positive PWID. This D2C intervention extends current efforts to improve the availability and use of data by assessing clients with standardized, validated assessments on a range

D2C Ukraine

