D2C is a structural intervention designed to sustainably change the HIV care providers' practices and facilitate information exchange at the facility level. To address the implementation science questions by measuring the provider-level outcomes and avoid contamination of the control condition due to unblinded allocation of intervention at the patient level, we propose a cluster-randomized trial design for this pilot study and the prospective RCT. We will select eligible HIV clinics (see "Study Sites," above) and randomly assign them 1:1 either to the intervention or the control arms. To achieve greater comparability between the arms, we will match pairs of eligible sites based on organizational context factors derived from Aim 1 data analysis, including facility size and type (e.g., NGO vs. public clinic), service delivery structure (e.g., social workers vs. nurses), and existing services for HIV-positive PWID (e.g. Steps Toward Health) and will randomize within the pairs. This will minimize the degree of between-cluster variation within the groups and increase power and precision.

Randomization will be conducted by the data manager using a computer program.

Sample size

We used methodology from Hayes et al⁸⁴ to determine the effect size that the intervention needs to demonstrate in a feasible matched-pair randomized trial. We assumed the cluster size of 75 patients (based on the optimal case manager workload) with 5 clusters per arm (potentially manageable number given the existing research infrastructure in Ukraine), coefficient of variation between clusters within matched pairs equal to 0.15 (empirically estimated based on the data from 56 clinics in the ART OPTI study, see Previous Studies), power of 80% and 0.05 significance level. Proportion of participants re-engaging into ART within 3 months after inclusion into the study was used as the key outcome. Under the assumptions, the relative difference between the study arms should be at least 22% (e.g. 50% vs 72%). The adjacent chart shows the power and sample size of a pilot trial needed to detect this difference with 0.05 significance level. To achieve 80% power, we will need to recruit 160 participants, or 80 per arm. We propose to divide the sample equally between 4 sites (2 per arm) to test the matching procedures. We do not adjust for loss-to-follow-up because for our main outcomes (ART initiation, viral suppression), loss to follow-up is equal to not achieving the outcome.

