We have powered this pilot study to evaluate feasibility of a prospective cluster RCT. The RCT will be considered feasible if the difference in the proportion of patients achieving the primary outcome (engagement in HIV care) will reach 22% between the study arms. We will estimate the impact of the intervention on the HIV care continuum using mixed effects models. For all outcomes, the data will have the same structure, with observations (t) nested within participants (i) nested within sites (j) nested within matched pairs (k). The correlations among observations will be addressed by using fixed-effects indicators for matched pair and normally distributed random intercepts for sites and for participants. Our mixed-effects models will include indicators for each of the two follow-up assessments, an indicator for site group assignment, and two group-assignment-by-follow-up interaction terms. We will also include sex/gender, age, and baseline covariates that have been identified in preliminary analyses as varying significantly across sites. A logit link function will be used for the primary outcome of ART (re-)initiation (defined above), and the coefficients for the two group-assignment-by-follow-up interaction terms will provide the estimates of the subject-specific intervention effects at 6 and 12 months post-baseline. We will examine the effects of sex/gender, age, substance use severity, ART history at baseline and other covariates in the multivariable models.

We will characterize patterns of behavior that impact HIV transmission (episodes of syringe sharing and episodes of unprotected intercourse in the prior 30 days without viral suppression) and we will use the same mixed-effects approach described above but with a log link function and negative

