binomial distribution. These analyses will provide parameters for estimating the rate of onward HIV transmission for the cost-threshold analysis. All analyses will include the use of the mixed effects "meqrlogit," "meologit," and "menbreg" procedures using Huber/White robust variance-covariance estimators. We will examine whether missingness is associated with observed data using standard methods.^{98–100} We will conduct a second set of outcome analyses using multiple imputation to evaluate the robustness of the primary outcome analyses to missingness and report estimates based on multiple imputation that would be valid based on the assumption that the data are missing at random (MAR). We will produce imputed datasets ($m > 10$) using chained equations,¹⁰¹ run outcome analyses on all sets, and derive point and standard error estimates for treatment effects and other parameters from the distribution of estimates from the outcome analyses with imputed datasets.

We will also evaluate the use of mixed proportional odds regression^{102,103} for determining whether intervention exposure is associated with an individual's location on five distinct stages of HIV care continuum: (1) not engaged in HIV care in the prior six months; (2) engaged in HIV care in the prior six months but no ART use in the prior 30 days; (3) ART use in the prior 30 days but no evidence of viral suppression in the prior 6 months; and (4) ART use in the prior 30 days with evidence of viral suppression in the prior 6 months. The HIV care continuum can be viewed as an ordinal categorical variable, and ordinal logistic regression will be used to evaluate if group assignment is associated with the location along the HIV care continuum. We will use the Score test to evaluate whether the proportional odds assumption of ordinal logistic regression.¹⁰⁴

These analyses will be essential for planning a full study. The findings will be used for sample size estimates, and data on HIV transmission risk will be used to determine whether the intervention could reasonably be cost-saving or cost-effective. This pilot analysis will provide important information on the feasibility of using ordinal logistic regression in a larger trial or in other analyses of the HIV care continuum.

Specific Aim 3a: To assess the feasibility, acceptability, and implementation-related processes and outcomes of the D2C strategy

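### The Score test is the only stated check on proportional odds; at 80 patients per arm it misses roughly 15–70% of relevant violations, so a non-significant result should not by itself support the model or a common odds ratio

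*Combined protocol and SAP*

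**What the plan says.** The Background (planning-grant paragraph) says the analytic strategy will help determine whether "mixed proportional odds models, may be suitable for modeling movement along the HIV care continuum among PWID". Under Specific Aim 2, Statistical Analysis and Feasibility Assessment, the ordinal model is evaluated in addition to the outcome models: "ordinal logistic regression will be used to evaluate if group assignment is associated with the location along the HIV care continuum". The check on its key assumption is one sentence, incomplete as printed: "We will use the Score test to evaluate whether the proportional odds assumption of ordinal logistic regression". The section closes with the intended use: "This pilot analysis will provide important information on the feasibility of using ordinal logistic regression in a larger trial".

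For this check the plan gives no significance level, acceptable departure, decision rule or fallback model. It does not say whether the test covers the arm term only or every covariate, at which follow-up it applies, or how it works with random intercepts and robust variances. It announces five stages and lists four.

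The sample size was set for something else, a difference in proportions: "To achieve 80% power, we will need to recruit 160 participants, or 80 per arm". Engagement, ART (re-)initiation and viral suppression are also defined as separate primary outcomes (Data Collection).

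**The concern.** A common odds ratio summarises the intervention effect only if that effect is about the same at each cut-point: engaged or better, on ART or better, suppressed. Concluding that it is the same is a claim of near-equality, and failing to reject equality does not establish that claim. The violation that matters here is easy to imagine: outreach brings patients back to visits and to ART but does not change suppression. If the test often misses that pattern at 160 patients, a non-significant result could be taken as support for the model when the larger trial is planned. A common odds ratio above 1 would then imply a gain at the suppression step that did not occur.

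**Working it through.** **1. The plan's own figure.** For 50% vs 72%, two-sided 0.05, 80% power, the mean proportion is 0.61:

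n per arm = [1.96·√(2·0.61·0.39) + 0.842·√(0.50·0.50 + 0.72·0.28)]² / 0.22² = (1.352 + 0.566)² / 0.0484 ≈ 76, or 152 in total.

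At 80 per arm the power is 0.82. So 160 is consistent with a simple two-proportion comparison, slightly rounded up. The plan states no power for the Score test.

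**2. Inputs for the Score test.**
- 80 per arm (Sample size).
- Four stages, as listed, giving 2 degrees of freedom for arm.
- Control distribution: not given for the trial. Assumed from the Background cascade for people who inject drugs: 52% in care, 38% on ART, 28% suppressed. An alternative of 75/60/40% is purely an assumption.
- 22-point engagement gain (Statistical Analysis and Feasibility Assessment).
- Assumed: test level 0.05, one visit, independent patients, no covariates, suppression unchanged.

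**3. Method.** For a 2×4 table the Score test equals the Pearson fit statistic of the fitted proportional-odds model. Applied to the expected counts, this statistic gives the noncentrality λ. The miss rate is P(χ²₂(λ) < 5.99). At 80 per arm:

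| Control → D2C (engaged/ART/suppressed, %) | True ORs | λ | Missed | Common OR |
|---|---|---|---|---|
| 52/38/28 → 74/60/28 | 2.63/2.45/1 | 9.95 | 19% | 1.89 |
| 52/38/28 → 74/49/28 | 2.63/1.57/1 | 7.44 | 32% | 1.72 |
| 52/38/28 → 74/38/28 | 2.63/1/1 | 10.55 | 16% | 1.58 |
| 52/38/28 → 68/52/28 | 1.96/1.77/1 | 4.99 | 50% | 1.56 |
| 52/38/28 → 63/49/28 | 1.57/1.57/1 | 3.08 | 67% | 1.38 |
| 75/60/40, ORs given | 2.57/2.57/1 | 8.29 | 27% | 1.51 |
| 75/60/40, ORs given | 2/2/1 | 4.99 | 50% | 1.37 |
| 75/60/40, ORs given | 2/1.5/1 | 3.04 | 67% | 1.28 |

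Simulated trials agree within about 3 percentage points, and the test's size under true proportional odds is about 5%. A few other assumed patterns fall just outside this range (12% and 76%).

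**4. Sensitivity.**
- A site random intercept with logit SD 0.3 moves the simulated miss rates by at most about 2 points.
- Two visits with an assumed correlation of 0.5 give an effective 80·2/1.5 ≈ 107 per arm. The 74/60/28 and 63/49/28 rows are then missed 8% and 57% of the time.
- A design effect of 1 + 39·0.0225 = 1.88 (coefficient of variation 0.15 at 50%, 40 per site) gives an effective 43 per arm. The same rows are missed 47% and 82% of the time.
- If the test is global over about 8 terms (16 df) and only arm violates the assumption, a λ of 6.35 (ORs 2/2/1 from 52/38/28) gives about 73% missed, against 39% on 2 df.

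**5. What the common OR would imply.** Control odds of suppression are 0.28/0.72 = 0.389. Multiplied by 1.58 and 1.89 they become 0.614 and 0.735, that is 38% and 42% suppressed, when the true figure is 28% in both arms.

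**6. Precision of a direct estimate.** For log(OR engaged / OR suppressed), each arm contributes [1/(e(1−e)) + 1/(s(1−s)) − 2/(e(1−s))]/80, where e is the proportion engaged and s the proportion suppressed.
- At 52/28: (4.006 + 4.960 − 5.342)/80 = 0.0453.
- At 74/28: (5.198 + 4.960 − 3.754)/80 = 0.0801.
- No effect in either arm: SE = √(0.0453 + 0.0453) = 0.30, so the 95% interval is ×/÷ 1.8.
- 22-point engagement gain, suppression unchanged: SE = √(0.0453 + 0.0801) = 0.35, so ×/÷ 2.0.

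**The case against.** The strongest reply is that the ordinal model is exploratory and additional. Suppression is a primary outcome in its own right, and mixed models are planned for all outcomes, so a nil suppression effect would be estimated directly. The stated go/no-go rule for the larger trial does not involve the Score test at all: "The RCT will be considered feasible if the difference in the proportion of patients achieving the primary outcome (engagement in HIV care) will reach 22" percent. When both engagement and ART rise by the planning effect of 22 points, the test does fairly well, missing about 15–20%.

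Most of this stands, and it rules out three stronger readings.
- A reader might infer that the trial will credit the intervention with false suppression gains. The documents do not support that: they make no suppression claim from the ordinal model. In the no-suppression patterns simulated, a significant common odds ratio together with a non-significant Score test occurs in only about 6–17% of trials.
- A reader might infer that p > 0.05 automatically means suitable. The plan states no such rule; the problem is that it states no rule at all.
- A reader might look for a single miss rate. None can be derived, because the trial's stage distribution is unknown. Recruitment draws on patients who had started ART and then missed visits, not on the national cascade.

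What does not stand is that the separate suppression outcome closes the gap. It uses viral loads over 12 months after enrolment, while the top ordinal stage combines ART use in the prior 30 days with suppression in the prior 6 months. Nothing requires the cut-point effects to be shown or compared, and an evaluation of the model still needs a basis for its conclusion.

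**Conclusion.** The point holds as a gap in how a stated product of the pilot will be judged. It is not a flaw in the primary analyses. With 80 per arm, a non-significant Score test leaves roughly a 15–70% chance that a violation with no suppression effect went unnoticed: about 15–35% at a 22-point engagement gain from the quoted cascade, more for smaller effects. These figures rest on one visit, independent patients, four stages, arm only and assumed control rates. Such a result should not by itself support the model or a common odds ratio. The appropriate response is a cheap improvement to the analysis text.

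**What to change.** - Fit the three cumulative logits (engaged or better, on ART or better, suppressed), or a partial proportional odds model, with the same pair and site terms as the other models.
- Report the arm odds ratio at each cut-point, and the ratio of the engagement to the suppression odds ratio, with 95% intervals beside any common odds ratio.
- Base the conclusion on suitability on these estimates and their intervals, not on the Score-test p-value.
- Draw no suppression claim from the common odds ratio; leave that to the primary suppression analysis.
- In the same edit, state the number of stages, the follow-up concerned, and whether any retained Score test covers arm only or all terms.

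The cost is a few lines of text and one extra model, with no new data. The downside is that, with the ratio known only to within about ×/÷ 1.8–2.0, the conclusion will often be inconclusive.

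A fixed pass margin would not help at this size. Take 0.5 to 2 as an example, with the whole 95% interval required inside it. An exactly proportional effect passes only if |log ratio| < 0.693 − 1.96·SE, which has a probability of about 27% at SE 0.30 and 2% at SE 0.35.

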
Specific Aim 3b: Economic Analyses To assess the costs and cost-threshold of the D2C strategy

In accordance with the recommendations of the 2nd U.S. Panel on Cost-Effectiveness in Health and Medicine,^{111,112} we will: inventory and value the resources consumed in the intervention; estimate intervention effectiveness in regards to HIV infections averted; estimate treatment costs averted and QALYs saved; and evaluate conditions under which the intervention would be cost-saving or cost-effective.

Cost analysis: We will estimate the cost of delivering the program locally from a societal perspective that incorporates broader costs, including non-medical costs to participants and costs reflected in the recently recommended impact inventory.¹¹² We will use micro-costing^{113,114} to directly enumerate every input used in the intervention such as staff time spent on each intervention activity, equipment, and materials. Any in-kind contributions will also be enumerated and costed. We will use both top-

down and bottom-up approaches,¹¹⁵ and sources of data will include project records, salaries, cost worksheets, project manager interviews, and a project manager survey. The program manager will complete a survey to quantify per unit costs for program resources, including procedure-specific resources, general resources, fixed resources, and variable resources. Participant time, travel, and any child or elder care will be measured and costed based on prevailing local wage. Cost data for each type of resource will include “best estimates” for cost and units consumed, and credible ranges to be used in sensitivity analyses will be established by asking program staff to provide upper and lower bounds for any uncertain cost estimates.

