Effectiveness, medical costs, and QALYs: Few HIV prevention studies are sufficiently powered to directly measure reductions in infections, and we will estimate HIV incidence among sexual and injection-drug-using partners under the standard of care scenario and under the intervention scenario using Bernoulli process models¹¹⁶ of injection drug use and sexual intercourse with behavioral patterns based on participant assessments and HIV transmission probabilities based on an updated review of the literature. The model will be based on participant data with a one-year timeframe for intervention costs and HIV transmission, and we will incorporate literature-based estimates of lifetime treatment costs and QALYs associated with new HIV infections in Ukraine, discounted at 3% per annum.^{111,117} Differences between the scenarios in estimated HIV transmission are expected to be driven primarily by ART use, but we will also incorporate observed data on intercourse, condom use, injection drug use, syringe sharing, and partner characteristics. The primary model will be based on the point estimates of parameters, but we will also conduct sensitivity analyses where input parameters are sampled from distributions that capture the uncertainty in our estimates. Many modeling approaches are available for modeling the incremental cost-effectiveness of D2C; given the exploratory nature of the proposed research, we believe a Bernoulli process model is appropriate.

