Incremental cost-effectiveness and threshold analyses: The cost-utility ratio will be computed based on the estimation of net incremental cost (i.e., difference between the incremental intervention costs and the incremental HIV treatment costs averted) divided by the QALYs averted. For a given model run, intervention will be considered: cost-saving if the incremental intervention cost is less than the incremental treatment cost averted; cost-effective if the net incremental cost per QALY saved is less than society’s willingness to pay to save one QALY; and not cost-effective if net incremental cost per QALY is greater than society’s willingness to pay.¹¹¹ The proportion of model runs that are cost-effective or cost-saving will be used to characterize the probability that the intervention meets these thresholds. We will also use one-way sensitivity analyses to identify conditions under which the intervention would be 90% likely to be cost-effective or cost-saving, such as specific intervention cost thresholds and intervention effectiveness thresholds.

Adverse events (including suicide risk)

The question 9 in PHQ-9 instrument may indicate suicidal thoughts among participants (“Thoughts that you would be better off dead or of hurting yourself in some way”). In case the participant responds anything except “not at all”, Interviewer asks an additional question: “In the last two weeks, have you had any thoughts of hurting yourself in some way?” (not at all, several days, more than half the days, nearly every day). If patient responds “not at all” to this question, the patient denies active suicidal thoughts. He or she is considered “very low or no risk” and no action is triggered at this point. If any other response is received, Interviewer will escort the patient to a clinician in the clinic for a formal assessment of suicide risk according to the national clinical standards (includes an assessment using the Columbia Suicide Severity Rating Scale). For those with a plan, the guidance stipulates that

patients will be transported emergently offsite to a psychiatric inpatient hospital for further evaluation and may be detained against their will for up to 72 hours.

Data management

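### The cost-saving rule credits the transmission benefit of extra ART but, as written, never charges for that ART

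*Combined protocol and SAP*

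**What the plan says.** All the relevant text is in Specific Aim 3b of the combined protocol and SAP.

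- **Effect measure.** The opening paragraph says the analysis will "estimate intervention effectiveness in regards to HIV infections averted".
- **Program cost.** Under Cost analysis, micro-costing will "directly enumerate every input used in the intervention such as staff time spent on each intervention activity, equipment, and materials". Participant time, travel and dependant care are added. A societal perspective is stated, but for the cost of delivering the program. ART drugs, clinic visits and laboratory tests are not named.
- **Treatment cost and QALYs.** Under Effectiveness, medical costs, and QALYs, the model uses a "one-year timeframe for intervention costs and HIV transmission" and takes in "literature-based estimates of lifetime treatment costs and QALYs associated with new HIV infections in Ukraine, discounted at 3% per annum". The same paragraph adds: "Differences between the scenarios in estimated HIV transmission are expected to be driven primarily by ART use".
- **Decision rule.** Under Incremental cost-effectiveness and threshold analyses, the numerator is the "difference between the incremental intervention costs and the incremental HIV treatment costs averted". A run is "cost-saving if the incremental intervention cost is less than the incremental treatment cost averted". The share of runs meeting each criterion is read as a probability, and one-way analyses then look for program-cost and effectiveness thresholds at which that probability is 90%.

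**The concern.** D2C is modelled as averting infections mainly by putting more participants on ART. That ART has to be paid for, as do the visits and tests that go with it. The rule counts the infections averted as savings and sets only program delivery cost against them. A program that raises total spending can then be labelled cost-saving.

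The stake is an Aim 3 deliverable. Specific Aim 3 promises thresholds for D2C to be cost-effective or cost-saving, and the Background says the cost work will show under what conditions D2C is a reasonable investment. Sampling inputs from distributions does not help, because a term missing from the formula is not an input that can be varied.

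**Working it through.** The plan states no unit cost, number of infections averted, ratio or willingness-to-pay value, so there is no economic figure to reproduce. The check is algebraic.

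**Notation**

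- I = program cost for the intervention arm.
- E = extra participant-years on ART.
- c = annual cost of ART and HIV care, assumed equal for participants and newly infected partners.
- r = infections averted per extra ART-year (assumed 0.01 to 0.10).
- L = years of treatment per new infection (assumed 10 to 40, starting at infection).
- D = 3% annuity over L years, payments at the start of each year.

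**Step 1: extra ART.** The Sample size section gives 80 per arm and an example of 50% versus 72% re-engaging in ART. If each extra person stays on ART for one year, E = 80 × (0.72 − 0.50) = 17.6, and the uncharged cost is 17.6c.

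**Step 2: the two rules.** Averted treatment cost is r × E × D × c.

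- As written: cost-saving if I < rEDc.
- With participants' ART charged: cost-saving if I + Ec < rEDc.

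They disagree when rEDc − Ec ≤ I < rEDc. In a given run the program-cost ceiling for cost-saving is overstated by Ec = 17.6c, or 17.6c/80 = 0.22c per participant, whatever r and L are. If rEDc < Ec, no program cost is low enough for D2C to be cost-saving.

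**Step 3: break-even.** Before any program cost, averted cost covers added ART only if rD ≥ 1, so r ≥ 1/D. E and c cancel.

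| L (years) | D | Break-even r | Averted cost, r = 0.02 | r = 0.05 | r = 0.10 |
|---|---|---|---|---|---|
| 10 | 8.79 | 0.114 | 3.09c | 7.73c | 15.46c |
| 20 | 15.32 | 0.065 | 5.39c | 13.48c | 26.97c |
| 30 | 20.19 | 0.050 | 7.11c | 17.77c | 35.53c |
| 40 | 23.81 | 0.042 | 8.38c | 20.95c | 41.90c |

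Each averted cost is compared with 17.6c of added ART. Over r = 0.01 to 0.10 the ratio of averted to added cost runs from 0.09 (1.55c/17.6c at L = 10, r = 0.01) to 2.38 (41.9c/17.6c at L = 40, r = 0.10). With end-of-year payments, D is 14.88 at 20 years and 19.60 at 30, and break-even r is 0.067 and 0.051.

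If r applies only to suppressed person-years, and about 74% of people who inject drugs on ART are undetectable (Background), break-even is 1/(0.74D): 0.088 at 20 years and 0.067 at 30.

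**Step 4: where the verdict is wrong, at L = 20**

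- r = 0.02: any program costing under 5.39c (5.39c/80 = 0.067c per participant) is called cost-saving, while total cost rises by 17.6c − 5.39c = 12.21c plus program cost.
- r = 0.05: any program under 13.48c is called cost-saving, while total cost rises by 4.12c plus program cost.
- r = 0.10: the verdict is wrong between 26.97c − 17.6c = 9.37c and 26.97c, or 0.117c to 0.337c per participant. Below 9.37c both rules correctly say cost-saving.

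**The case against.** A reader might infer that the plan definitely excludes participants' ART cost. The wording does not go that far. The averted treatment cost is called incremental, so it could be meant as a net difference between scenarios. Lifetime costs of new infections are named as an input, not as the only treatment cost. The section also commits to the U.S. Panel's recommendations, a societal perspective and the impact inventory. But no text states the netting, the perspective is attached to program delivery, and the formula does not carry it through. The rule as written still gives the wrong answer, whatever was intended.

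A reader might also infer that D2C will be falsely declared cost-saving. The documents do not show this. The false verdict needs program cost to fall inside a bounded window, and at low r that window sits at a small fraction of one year's ART cost. D2C involves home visits, outreach through NGOs and reassessment every 3 months, and no cost for it is given. A costlier program fails both versions of the rule.

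A third tempting inference is that the cost-per-QALY ratio favours D2C too. It may not: leaving out participants' ART cost helps D2C, while leaving out their QALY gain counts against it.

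Finally, this is a pilot and the plan calls its economic modelling exploratory. That limits the consequence, but thresholds are still a named output.

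**Conclusion.** The point stands for the cost-saving rule. If D2C raises ART use, the stated rule errs in one direction: it can call a cost-raising program cost-saving and cannot do the reverse. A run is misclassified when program cost is below averted treatment cost but not below averted cost minus added ART cost. Added ART cost alone exceeds averted cost when r is below about 0.05 to 0.07, for 20 to 30 years of treatment.

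The break-even rests on equal annual cost for participants and new infections, 3% discounting and the assumed L. The range of r is also assumed, since the documents give none. The 17.6c rests on the 22-point planning example, which concerns re-engagement within 3 months, and on one year of ART per extra person. Shorter exposure scales both sides and leaves the break-even unchanged.

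For the cost-per-QALY rule, the ratio is incomplete in both numerator and denominator, and the direction of the net error is not determined.

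**What to change.** Define net incremental cost as program cost, plus participants' incremental ART and HIV-care cost, minus lifetime treatment cost of infections averted. Use it in both the cost-saving and the cost-effective rules, and so in the threshold analyses.

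Quantities can come from the medical information system, which holds prescriptions, appointments kept and laboratory results and is already extracted monthly. Unit costs for drugs, visits and tests would come from local or literature sources, because none of the cost sources now named is said to supply them.

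Add participants' QALY change to the denominator over the same horizon as their costs. Within the year, use the SF-12 collected at baseline, 6 and 12 months, with a stated mapping to utilities. The plan gives no mapping, and a 12-month change alone does not match the lifetime horizon used for averted infections. If participants' costs and QALYs are extended beyond the year, use literature values for both. Keep the transmission-only version as a sensitivity analysis.

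The cost is revised wording, a few added unit-cost and utility inputs, and a cost-saving verdict that is harder to reach. Sample size, visits and participant burden do not change.
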